#### *Hepatic events:*

If AST and/or ALT are increased  $\geq 3$  x ULN, follow-up laboratory tests of ALT, AST, total bilirubin (with differentiation of bilirubin in direct and indirect if total bilirubin is elevated) and additionally alkaline phosphates (ALP), CK (CK-MB if CK is elevated), amylase, lipase and INR must be initiated as soon as possible (ideally within 48 to 72 hours of the pathologic test result). Further follow-up investigations shall be initiated depending on the clinical course until the patient is recovered and/or a diagnosis was made. See for further details [Section 10.6.2](#).

Laboratory Criteria for "Potential Hy's Law case":

1. AST and/or ALT  $> 3$  x ULN and
2. Total bilirubin  $> 2$  x ULN and
3. ALP  $< 2$  x ULN

*Renal events:*

If creatinine shows a  $\geq 2$ -fold increase from baseline, the investigator should make arrangements for follow-up blood samples(s) to be collected for repeat analysis of creatinine.

Further follow-up investigations should be done according to medical judgement depending on the clinical course until the patient is recovered and/or a diagnosis is made.

*Skin lesions:*

If skin lesions (such as exfoliative rash, skin necrosis, or bullous dermatitis - see further detailed list in ISF): further follow-up investigations should be done according to medical judgement depending on the clinical course until the patient is recovered and/or a diagnosis is made.

Protocol-specified AESIs (as identified by the investigator based on the above definitions for adverse events of special interest) can be classified as serious or non-serious but all these AESIs once identified by the investigator must be reported on an SAE form in an expedited manner similar to SAEs, even if they do not meet any of the SAE seriousness criteria.

Beyond of this, and for the purposes of ongoing pharmacovigilance activities by the sponsor, adverse events based on additional searches for coded preferred terms of adverse events captured in the trial database (such as Special MedDRA Queries (SMQs), and user defined searches (BicMQs)) will be queried to verify with the investigator if the adverse event reported represent such a suspected or diagnosed protocol specific AESI. AESIs once identified by the investigator must be reported on a SAE form in an expedited manner similar to SAEs, even if they do not meet any of the SAE seriousness criteria.

These additional searches (summarised under the so called 'overview of protocol defined AESIs and safety topics of interest ') may change according to active pharmacovigilance of linagliptin. The most up to date list of these searches will be included in the ISF/Remote Data Capture (RDC) system and changes will be communicated to all investigators.

#### 5.2.2.2 Adverse event and serious adverse event reporting

Reporting will be done according to the specific definitions and instructions detailed in the 'Adverse Event Reporting' section of the Investigator Site File (ISF).

All adverse events, serious and non-serious and all AESIs, occurring during the course of the clinical trial (i.e., from signing the informed consent onwards through the residual effect period (REP) until the individual patient's end of trial) will be collected, documented and reported to the sponsor by the investigator on the appropriate eCRFs pages.

The REP (timeframe after last dose of study medication when measurable drug levels or pharmacodynamic effects are still likely to be present) is defined as 7 days after the last trial medication application. All AEs which occurred through the treatment phase and throughout the REP will be considered as on treatment please see [section 7.3.3](#). Events which occurred after the REP will be considered as post treatment events.

After the individual patient's end of trial the investigator does not need to actively monitor the patient for AEs but should only report relevant SAEs and relevant AESIs of which the investigator may become aware of.

However, if in an individual patient only vital status information is collected after premature discontinuation, from then on and until the individual patient's end of trial, the investigator does not need to actively monitor the patient for AEs but should only report fatal AEs, relevant SAEs and relevant AESIs of which the investigator may become aware of.

Immediate documentation of events:

The investigator must report immediately (within 24 hours of awareness the following events on the SAE form to the sponsor's unique entry point as specified in the ISF:

- All SAEs
- All serious and non-serious AESIs
- Non-serious AEs relevant for a reported SAE(s) and/or AESI(s)
- Potential Hy's Law cases (see Section [5.2.2.1](#))
- Cardiovascular outcome events if they represent a SAE and occur during the screening/run-in phase

The same timeline applies if follow-up information becomes available. In specific occasions the Investigator could inform the Sponsor upfront via telephone. This does not replace the requirement to complete and fax the BI SAE form.

#### *AEs considered "Always Serious"*

In accordance with the European Medicines Agency initiative on Important Medical Events, Boehringer Ingelheim has set up a list of AEs, which by their nature, can always be considered to be "serious" even though they may not have met the criteria of an SAE as given above.

BI has established a list of AEs which are defined to be always serious. In order to support the investigator with the identification of these "always serious adverse events", if a non-serious AE is identified to be serious per BI definition, a query will be raised. The investigator must verify the description and seriousness of the event. If the event description is correct, the item "serious" needs to be ticked and a SAE has to be reported in expedited fashion following the same procedure as above.

The list of these adverse events can be found via the RDC-system.

*For Japan: This information must be also reported immediately to the head of the trial site.*

### Information required

For each AE, the Investigator should provide the information requested on the appropriate (e)CRF pages and the BI SAE form, e.g. onset, end date, intensity, treatment required, outcome, seriousness, and action taken with the investigational drug(s). The Investigator should determine the causal relationship to the trial medication, and any possible interactions between the investigational drug(s) and a Non-Investigational Medicinal Product (NIMP).

All (S)AEs, including those persisting after individual patient's end of trial must be followed up until they have resolved, have been sufficiently characterized, or no further information can be obtained.

This immediate report is required irrespective of whether the investigational product has been administered or not and irrespective of causal relationship. It also applies if new information to existing SAEs or protocol-specified AESIs becomes available.

### Pregnancy

In rare cases, pregnancy might occur in clinical trials. Once a female subject has been enrolled into the clinical trial, after having taken study medication, the investigator must report immediately any drug exposure during pregnancy to the sponsor. Drug exposure during pregnancy has to be reported immediately (within 24 hours of awareness to the defined unique entry point for SAE forms of the respective BI OPU (country-specific contact details will be provided in the Investigator Site File). The outcome of the pregnancy associated with the drug exposure during pregnancy must be followed up. In the absence of an (S)AE, only the Pregnancy Monitoring Form for Clinical Trials and not the SAE form is to be completed. The ISF will contain the Pregnancy Monitoring Form for Clinical Trials (Part A and Part B).

#### 5.2.2.3 Oncological adverse events

Epidemiological evidence suggests that people with diabetes are at a significantly higher risk of several forms of cancer compared with subjects without diabetes [[R10-6495](#)]. Currently it is unclear whether the association between cancer and diabetes is indirect and largely due to shared risk factors (such as the modifiable risk factors: e.g. obesity, diet, physical activity, tobacco smoking, alcohol, or non-modifiable risk factors: e.g. age, gender, race, and ethnicity), whether it is direct influence (e.g. due to hyperglycaemia), or whether diabetes is a marker of underlying biologic factors that alter cancer risk (e.g. insulin resistance and hyperinsulinemia) [[R10-6496](#), [R10-6498](#), [R10-6536](#), [R10-6497](#), [R10-6494](#)].

In order to assess patients with oncological adverse events (benign and malignant) in detail, detailed information will be requested and should be provided. The main focus on oncological adverse events is on the following organ systems, based on [[R10-6638](#)] where an increased risk for cancer in the population of patients with T2DM was described:

- Liver
- Pancreas
- Endometrium

Proprietary confidential information.

© 2019 Boehringer Ingelheim International GmbH or one or more of its affiliated companies. All rights reserved.

This document may not - in full or in part - be passed on, reproduced, published or otherwise used without prior written permission.

- Colon and rectum
- Breast
- Bladder
- Thyroid
- Prostate

Request for detailed information (e.g. medical history, diagnostic result, laboratory results staging, genetics), will be mainly focused on the above listed organ systems, however is not restricted to them. For details refer to the oncology assessment charter.

### 5.2.3 Assessment of safety laboratory parameters

The parameters that will be determined are listed below. Analysis will be performed by a central laboratory:

#### 5.2.3.1 Haematology

- Haematocrit
- Haemoglobin
- Erythrocyte count
- Platelet count
- Total and automates differential leukocyte counts (Neutrophils, Eosinophils, Basophils, Lymphocytes, Monocytes) in absolute counts

#### 5.2.3.2 Clinical chemistry

- Amylase
- Lipase
- AST\*\* (aspartate transaminase, SGOT)
- ALT\*\* (alanine transaminase, SGPT)
- $\gamma$ -GT (gamma-glutamyl-transferase)
- Alkaline phosphatase
- Lactic dehydrogenase (LDH)
- Total bilirubin\*\*
- Direct and indirect bilirubin if total bilirubin is elevated
- Total Protein
- Albumin
- Creatine kinase (CK)
- CK-MB, if CK is elevated
- Potassium
- Sodium
- Creatinine
- Urea
- Calcium
- Inorganic phosphorous
- Urid acid
- Cholesterol (total)\*\*\*
- HDL cholesterol\*\*\*
- LDL cholesterol\*\*\*
- Triglycerides\*\*\*
- Troponin

\*\*AST, ALT and Total bilirubin are combined in any lab assessment, with exception of Visit 1a.

\*\*\* Lipid profile, only obtained at Visits 2, 6, 9, 12, 15, 18, 21, 24, 27, ~~and~~ 30 and 32.

Proprietary confidential information.

© 2019 Boehringer Ingelheim International GmbH or one or more of its affiliated companies. All rights reserved.

This document may not - in full or in part - be passed on, reproduced, published or otherwise used without prior written permission.

#### 5.2.3.3 Urinalysis

- Albumin, Creatinine (spot urine – quantitative measurement)
- Protein
- Ketone
- Leucocytes

Visit 1a safety laboratory only includes ALT (SGPT), AST (SGOT), alkaline phosphatase, serum creatinine, urine analysis and urine albumin and creatinine, in addition to HbA1c and does not need to be collected in fasted state.

Exact date and time of blood sampling should be recorded on the central laboratory requisition form.

Albumin/creatinine ratio will be calculated at the central lab.

Pregnancy testing (urine dipstick method) will be performed in female patients of child-bearing potential according to the [Flow Chart](#). Testing will be performed locally, using pregnancy test kits provided by the central laboratory.

Immediately after the result of a pregnancy test is known, the pregnancy test kit will be discarded at the site. The result of the test must therefore be documented in the source documents available at site for future verification by the on-site monitor.

A negative pregnancy test result is required at Visit 2 for all female patients of childbearing potential to remain eligible for entry into the treatment phase of the trial.

#### 5.2.3.4 Renal function impairment

Renal function impairment will be assessed by the central lab based on the plasma creatinine value measured according to the Flow Chart.

Estimated Creatinine clearance will be calculated from serum creatinine using the following MDRD formula as specified in the Statistical Analysis Plan.

This formula considers the race as an adjustment factor, therefore, the race must be known (and will be collected) for accurate estimation.

Renal impairment will be classified in the following way:

- No renal function impairment: eGFR  $\geq 90$  mL/min/1.73m^2;
- Mild renal function impairment: eGFR 60-89 mL/min/1.73m^2;
- Moderate renal function impairment: eGFR 30-59 mL/min/1.73m^2;
- Severe renal function impairment: eGFR 15-29 mL/min/1.73m^2;
- Kidney failure: eGFR  $< 15$  mL/min/1.73m^2.

#### 5.2.4 Electrocardiogram (ECG)

12-lead ECGs (I, II, III, aVR, aVL, aVF, V1 - V6) will be recorded according to the [Flow Chart](#).

The ECGs will be centrally analysed and stored by third party. Investigators will receive evaluated ECGs within 3 working days by third party, unless there are unresolved discrepancies. Additional ECGs may be collected by the investigator for safety reasons. Clinically relevant abnormal findings will be reported as AEs, if they are newly discovered after inclusion in the trial.

The recordings will be checked for pathological results by the investigator. Any ECG abnormalities will be carefully monitored and, if necessary, the patient will be removed from the trial and medically treated.

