### 3.3.4 Removal of patients from therapy or assessments

#### 3.3.4.1 Removal of individual patients

This is a long-term safety outcome study and every effort should be made by the site staff to encourage patients to remain in the study and on study drug if medically safe. Patients who prematurely discontinue study drug should remain in the study and should be observed until study end, preferably at the study time points as pointed out in the [Flow Chart](#).

If a patient who prematurely discontinued study drug is not willing to return at the pre-defined regular visit schedule, at minimum a yearly telephone call (preferably every 6 months) and a telephone call at study end (through the patient or alternative person designated by the patient) will be required, to document the occurrence of outcome events and vital status. If possible, also other AE's and concomitant therapy changes since last visit should be recorded. Every attempt will be made by the investigator to ensure patients continue participating in the study during study drug interruptions and after discontinuation of study drug.

Patients who prematurely discontinue study medication are allowed to restart the study medication at any time if appropriate in the opinion of the investigator and if not contraindicated. In this study, patients are allowed to have multiple study drug interruptions. There is no limit on either the number of study drug interruptions or the maximum length of any study drug interruption. Investigators should routinely consider re-starting study drug at every visit following study drug discontinuation.

A patient could be instructed to stop the study drug only after discussion between sponsor representative and investigator, if eligibility criteria are being violated, or if the patient fails to comply with the protocol (e.g. non-attendance at study assessments). Early discontinuation of study medication is not a criterion for withdrawal of consent for participating in the study.

If determined by investigator as necessary for patient safety, new antidiabetic medication regimen can be started immediately after discontinuation of study treatment and must be recorded in the eCRF (see further details in [Section 4.2](#)).

If a patient becomes pregnant during the trial the study treatment will be stopped, the patient will be followed up during the study and until birth or otherwise termination of the pregnancy (see further details in [Section 5.2.2.2](#))

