If pancreatitis is suspected, the study treatment should be stopped.

Patients who drop out during the screening/run-in phase prior to randomisation (Visit 2) will be considered a screening failure. They have to be recorded as screening failure in eCRFs and no further follow-up is required.

Patients who withdraw or discontinue from the study after randomisation will not be replaced.

If a patient needs to take concomitant drugs that interfere with the investigational product (or other study medications) or in the occurrence of hypoglycaemia that may put the patient at risk with continued participation (e.g. repeated hypoglycaemic episodes) the trial medication can be discontinued temporarily, or if needed permanently. Since this is an outcome study, the primary analysis will be performed based on all randomised patients who were treated with at least one dose of study drug. Therefore investigators are encouraged to re-administer study medication to a randomised patient if there are no further safety concerns.

A patient has the right to withdraw informed consent for participation at any time for any reason. However, withdrawal of consent from study participation should be very rare and unusual. Because of this, the investigator must be involved in the discussions with the patient regarding a withdrawal of consent.

If the patient withdrew informed consent the patient should stop taking study medication and should be asked to complete the study ending tests and procedures as described in the [Flow Chart](#) for End of Treatment Visit and Visit 33 (Follow up visit). Completing these procedures is strongly recommended for the patient's safety. The

reason for discontinuing treatment will be recorded in the eCRF. The data will be included in the trial database and will be reported.

For patients that have withdrawn informed consent, the patient will be asked to resign an informed consent form, which will allow to enquire at least about the patient's vital status and occurred outcome events through contacts to relatives, acquaintances, family physicians, hospital records, etc.

If patients who discontinue from treatment after randomisation could not be followed-up until the end of study (i.e. at least the vital status could not be collected) those patients will be indicated as Lost To Follow Up (LTFU). The number of LTFU patients should be limited.

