The use of rescue medication has to be taken in accordance with the prescribing information and will be recorded in the eCRF. Patients who have to be treated with other rescue medication than the protocol defined rescue therapy should discontinue study treatment when the combined use of the study treatment and this rescue medication is contraindicated, but will remain in the trial.

Any additional treatment, that does not qualify as a rescue medication, and is considered necessary for the patient's welfare may be given at the discretion of the investigator. Exceptions to this are the restrictions described in Section [4.2.2](#).

All concomitant (additional) and/or rescue medication will be recorded on the appropriate pages of the eCRF.

There are no special emergency procedures to be followed.

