## 6.2.2 Treatment phase

Randomisation will occur at Visit 2 using IXRS.

The patients will return to the clinic for regularly scheduled visits as specified in the [Flow Chart](#). These visits will assess the occurrence of safety and efficacy endpoints, study medication compliance and accountability, concomitant therapy or intervention. Between Visit 2 and Visit 6 glimepiride/glimepiride placebo will be uptitrated up to maximal 4 mg/day ([refer to section 4.1.4](#)).

At each visit trial medication compliance will be calculated and new supplies from a new medication kit assigned via IXRS will be dispensed.

This is an outcome study. All patients, including those who discontinue treatment must be followed up until the end of the study. Patients who prematurely discontinue treatment will continue to be contacted by the investigator at regular intervals (according to the original visit schedule or an alternative reduced schedule negotiated with the patient). If a patient who prematurely discontinued study drug is not willing to return at the pre-defined regular visit schedule, at minimum a yearly telephone call (preferably every 6 months) and a telephone call at study end (through the patient or alternative person designated by the patient) will be required, to document the occurrence of outcome events and vital status. If possible, also other AE's and concomitant therapy changes since last visit should be recorded. Every attempt will be made by the investigator to ensure patients continue participating in the study during study drug interruptions and after discontinuation of study drug.

Patients who prematurely discontinued study medication during the Maintenance Phase are allowed to restart the study medication at any time. Every attempt should be made by the investigator to have the patient restart study medication, even if the dose must be ~~down~~ titrated.

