#### Primary endpoint

The primary endpoint used in the primary analysis is time to the first occurrence of any of the following adjudicated components of the primary composite endpoint: CV death (including fatal stroke and fatal MI), non-fatal MI (excluding silent MI) or non-fatal stroke.

If patients do not experience a primary endpoint event, they will be considered censored at their last documented study visit. If a patient died and has no primary outcome event, the patient will be censored at the date of death.

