### **6.8.3 Censoring**

*Primary, key secondary, secondary CV and tertiary CV endpoints (except stand-alone endpoints of CV death, all-cause mortality, non CV-death and silent MI) and time to first disabling or fatal stroke*

The underlying principle is that the censoring date should be the last date a patient was known to be free of an endpoint event (e.g. free of each component of the 4P-MACE).

Patients without occurrence of a specific endpoint (composite endpoint or individual components) will be considered censored at their last documented study visit\*.

\* This includes any dates as of

- adverse event/outcome event start dates (if non-fatal events),
- onset dates of adjudicated (confirmed and non-confirmed) events (if non-fatal event),
- date of PCI/CABG
- date of trial completion (defined as latest of date of last clinic visit, last telephone call, date of last contact if lost to follow-up).

Censoring is considered independent from study drug intake.  
Any information as permitted by local law will be used in the analyses.

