### **7.4 PRIMARY ENDPOINT**

#### **7.4.1 Primary analysis**

For the primary endpoint of time to the first occurrence of any of the following CEC confirmed adjudicated components of the primary composite endpoint: CV death (including

fatal stroke and fatal MI), non-fatal MI (excluding silent MI), or non-fatal stroke an ITT-analysis (as randomised) on the TS will be performed. The analysis will be performed on TS with patients considered as randomised (intention-to-treat) and all events up to individual day of trial completion considered.

The randomised study treatment will be used to assign patients and events to treatment groups; all adjudicated events which occur until study end will be taken into account (i.e. independent of whether or not a patient was still on study medication).

The time to the primary endpoint will be derived from the date of randomisation.

The one-sided overall significance level will be  $\alpha=2.5\%$ . As described in the CTP, the DMC will perform formal interim analyses. The significance levels for the analyses are denoted by  $\alpha_i$ ,  $i=1, \dots, K$ , where K is the total number of analyses.

The O'Brien & Fleming alpha-spending function defined the significance level for the first interim analysis on 4P-MACE.

Due to the change of the primary endpoint after the first DMC interim analysis a Bonferroni adjustment will be applied in addition, to control the overall alpha level.

That means, the alpha spent at the first DMC interim analysis (performed for 4P-MACE and based on the O'Brien & Fleming alpha-spending function) is subtracted from the initial overall alpha. The O'Brien & Fleming alpha spending function based on the new overall alpha (after additional Bonferroni adjustment) defines the allocation of the still available overall significance level for the second interim analysis and the final analysis.

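### Protocol 5.2.4 allows removal from the trial for an ECG abnormality, which contradicts the rule in 3.3.4.1 and 6.2.2 that every patient is followed to study end; the passages need to be reconciled.

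*Protocol*

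**What the plan says.** Protocol 5.2.4, on the scheduled 12-lead ECGs: "Any ECG abnormalities will be carefully monitored and, if necessary, the patient will be removed from the trial and medically treated". The object of removal is the trial; study drug is not mentioned.

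The follow-up rule points the other way:

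- Protocol 6.2.2: "All patients, including those who discontinue treatment must be followed up until the end of the study".
- Protocol 3.3.4.1: "Patients who prematurely discontinue study drug should remain in the study and should be observed until study end". The same section, footnote N of the Flow Chart and section 3.1 all set a minimum of a yearly telephone call and a call at study end, to collect outcome events and vital status.
- Protocol 4.2.1, for patients who must stop study drug because of a contraindicated rescue medication: they stop treatment "but will remain in the trial".

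On the analysis side:

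- SAP 7.4.1: "all adjudicated events which occur until study end will be taken into account", whether or not the patient is still taking study drug.
- Protocol 7.1, for patients without a primary event: "they will be considered censored at their last documented study visit".
- SAP 6.8.3: "The underlying principle is that the censoring date should be the last date a patient was known to be free of an endpoint event".
- Protocol 3.3.4.1: "Patients who withdraw or discontinue from the study after randomisation will not be replaced".

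**The concern.** A site cannot both take a patient out of the trial and follow that patient to study end. The trigger in 5.2.4 is a cardiac finding, and the primary endpoint is CV death, non-fatal MI or non-fatal stroke. Patients removed on that trigger plausibly carry more than average risk of the endpoint. That is an inference; the documents give no risk figure.

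Censoring such patients would be informative, and it would cut across the intention-to-treat principle of SAP 7.4.1. The planned sensitivity analyses in SAP 7.4.2.2 would not repair it, because each of them shortens follow-up relative to the primary analysis. None recovers events that occur after a patient has left the trial.

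**Working it through.** **Text comparison.** The Flow Chart schedules ECGs at Visit 2 and then at Visits 6, 9, 12, 15, 18, 21, 24, 27, 30 and 32. Ten of the eleven therefore fall after randomisation, so 5.2.4 bears mainly on randomised patients. The section on removal of individual patients (3.3.4.1) names no ECG ground for ending follow-up. For other safety triggers the protocol refers to study treatment: suspected pancreatitis (3.3.4.1), contraindicated rescue medication (4.2.1) and liver injury (10.6.3). Section 5.2.4 is the exception, and no other passage qualifies it.

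**The plan's own figures (Protocol 7.6).** Inputs: 631 events, margin 1.3, one-sided alpha 2.5%, 1:1 allocation.

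- Non-inferiority power = Φ(ln 1.3 × √631 / 2 − 1.960) = Φ(3.295 − 1.960) = 0.909. Stated: 90.9%.
- Expected events with 6000 patients, a 1-year event rate of 0.018 in both arms, 1.5% yearly loss, 2 years of uniform accrual and 5.4 years of further follow-up: 627.7, against a target of 631.

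Both reproduce. This point disputes no design figure.

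**Events that would go uncounted.** Planned hazard: −ln(1 − 0.018) = 0.01816 per year. Mean follow-up: 5.4 + 2/2 = 6.4 years, so removal midway leaves 3.2 years unobserved. The proportion removed (p) and the relative hazard after removal (k) are assumptions.

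Events uncounted = 6000 × p × (1 − exp(−k × 0.01816 × 3.2))

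| p | k | Events uncounted | Share of 631 |
|---|---|---|---|
| 1% | 2 | 6.6 | 1.0% |
| 1% | 3 | 9.6 | 1.5% |
| 3% | 2 | 19.8 | 3.1% |
| 3% | 3 | 28.8 | 4.6% |

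A second calculation allowed for loss to follow-up, put removal at year 3 and used a wider range (p from 0.5% to 5%, k from 1 to 3). It gives 1.6 to 44.7 events uncounted. If none were made up, non-inferiority power would be between 90.8% and 88.8%. At the worst corner: Φ(ln 1.3 × √586.3 / 2 − 1.960) = 0.888.

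**Effect on the hazard ratio.** With a true ratio of 1.0 and equal removal in both arms, the observed rate ratio stays at 1.00. Suppose instead that one arm loses five events more than the other, out of 631/2 = 315.5 per arm.

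- Events in that arm fall by 5/315.5 = 1.58%.
- Censoring also removes person-time: 1.58%/k, which is 0.79% for k = 2 and 0.53% for k = 3.
- Net shift: 1 − 0.9842/0.9921 = 0.8% (k = 2); 1 − 0.9842/0.9947 = 1.1% (k = 3).

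Five extra events require 5/(1 − exp(−2 × 0.01816 × 3.2)) ≈ 46 extra removals in one arm at k = 2, or about 31 at k = 3.

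The second calculation with unequal removal (linagliptin 2% against glimepiride 1%, up to 5% against 1%, k of 2 to 3) shows a full-follow-up rate ratio of 1.005 to 1.038 being observed as 1.00. An excess of removals on linagliptin would thus favour non-inferiority; an excess on glimepiride would act against it.

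**The case against.** The strongest reply is that 5.2.4 is loose wording for stopping study drug. Removal is conditional on being judged necessary, the follow-up rule is stated several times, and scheduled ECGs cease once drug is stopped, so the sentence concerns patients on treatment. That reading is plausible, and nothing shows that any site would act otherwise. But the text does not say so, and sites act on the text.

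Second, some feared losses would not occur. ECG signs of silent MI are reported as outcome events (Protocol 5.2.2.1), and a reported silent MI that the adjudication committee confirms as an MI counts as one (SAP 5.1). For that patient the first primary event has already happened, and later removal changes nothing. The formula above ignores this, so it errs on the high side.

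Third, the trial is event-driven: Protocol 3.1 extends duration or enrolment until the target is reached, and 7.3.4 sets a minimum of 631 events for the final analysis. A reader might infer from the uncounted events that power is materially lost. The documents do not support that; the main cost would be time. The plan also already allows for 1.5% loss per year.

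Fourth, the study is double-blind and double-dummy. At 1% removal (60 patients), a five-event imbalance would need a split of roughly 53 against 7 (k = 2) or 46 against 14 (k = 3), and nothing in the documents suggests one.

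These replies limit the size of the effect. They do not remove the contradiction.

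**Conclusion.** The contradiction is real and stands in current operative text. Its consequence is conditional: a site would have to judge removal necessary and read the sentence as ending follow-up. A reader might infer that the plan as written does censor high-risk patients; the documents show only that it permits this.

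The likely size is small. The 7-29 uncounted events rest wholly on assumed removal rates and hazards, with removal midway through follow-up. A reader might also take five lost events out of 315.5 as a 1.6% shift in the hazard ratio. That leaves the removed patients' person-time in the denominator; counting it gives 0.8-1.1%, and only if removals, or the risk of those removed, differ by arm.

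The point still deserves action. The trigger is cardiac, the direction of any imbalance cannot be known in advance, and no planned analysis would recover the missing follow-up.

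**What to change.** Reconcile 5.2.4 with 3.3.4.1 and 6.2.2. State whether 5.2.4 concerns study drug or trial participation, so that the text agrees with the protocol's own rule on follow-up for outcome events and vital status. How the ECG finding itself is managed is a clinical matter for the sponsor and is not prescribed here.

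Cost: one sentence in the protocol, or a letter to sites. No new procedure, visit or analysis is needed.
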